6.3 Randomization

In Part A, Groups 1 and 3 will be randomized and will enroll no more than 1 participant per day for 3 participants per group. Contingent on the safety data from Groups 1 and 3, Groups 2, 4, and 5 will be randomized and may enroll simultaneously with no more than 1 participant per day for 3 participants for each group. Contingent on the safety data from Groups 1-5 in Part A, Groups 6-8 in Part B will be randomized and stratified by whether or not participants will be willing to consent to leukapheresis. A maximum of 7 participants per group that do NOT consent to leukapheresis collection will be enrolled. A participant's randomization assignment will be computer generated and provided to the HVTN CRS pharmacist through a Web-based randomization system. At each institution, the pharmacist with primary responsibility for dispensing study products is charged with maintaining security of the treatment assignments (except in emergency situations as specified in the HVTN manual of procedures [MOP]).

6.4 Blinding

Participants and site staff will be unblinded to participants' group assignments. Laboratory program staff will be unblinded to whether a sample is from Part A or Part B but will remain blinded to the treatment assignment within Part A or Part B during assay analysis.

6.5 Statistical analyses

This section describes the final study analyses, unblinded as to treatment arm assignment. All data from enrolled participants will be analyzed according to the initial randomization assignment regardless of how many vaccinations they received. In the rare instance that a participant receives the wrong treatment at a specific vaccination time, the Statistical Analysis Plan (SAP) will address how to analyze the participant's safety data. Analyses are modified intent-to-treat in that individuals who are randomized but not enrolled do not contribute data and hence

are excluded. Because of the brief length of time between randomization and enrollment (typically no more than 4 working days), very few such individuals are expected.

Analyses for primary endpoints will be performed using statistical analysis system (SAS) and R. All other descriptive and inferential statistical analyses will be performed using SAS, StatXact, or R statistical software.

No formal multiple comparison adjustments will be employed for multiple safety endpoints, multiple primary immunogenicity endpoints, or secondary endpoints. However, multiplicity adjustments will be made for certain immunogenicity assays, as discussed below, when the assay endpoint is viewed as a collection of hypotheses (eg, testing multiple peptide pools to determine a positive response).

6.5.1 Analysis variables

The analysis variables consist of baseline participant characteristics, safety, and immunogenicity for primary- and secondary-objective analyses.

6.5.2 Baseline comparability

Treatment arms will be compared for baseline participant characteristics using descriptive statistics.

6.5.3 Safety/tolerability analysis

Since enrollment is concurrent with receiving the first vaccination, all participants will have received at least 1 vaccination and therefore will provide some safety data.

6.5.3.1 Reactogenicity

The number and percentage of participants experiencing each type of reactogenicity sign or symptom will be tabulated by severity and treatment arm in Part A and Part B and the percentages displayed graphically by arm. For a given sign or symptom, each participant's reactogenicity will be counted once under the maximum severity for all injection visits. In addition, to the individual types of events, the maximum severity of local pain or tenderness, induration or erythema, and of systemic symptoms will be calculated. Kruskal-Wallis tests will be used to test for differences in severity across arms and Wilcoxon rank sum test will be used to test for difference in severity between 2 arms in Part B.

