HIV VACCINE
TRIALS NETWORK

PROTOCOL

HVTN 303

A Phase 1, Open-Label Clinical Trial to Evaluate Safety, Tolerability, and Immunogenicity of Adjuvanted HIV-1 Fusion Peptide Conjugate Vaccine (VRC-HIVVCP0108-00-VP) Alone or in Prime-Boost Regimens with Adjuvanted HIV-1 Envelope Trimer 4571 (VRC-HIVRGP096-00-VP) and HIV-1 Trimer 6931 (VRC-HIVRGP0106-00-VP) Vaccines in Healthy Adults

DAIDS DOCUMENT ID 38835

IND 028412 HELD BY DAIDS

CLINICAL TRIAL SPONSORED BY

Division of AIDS (DAIDS)
National Institute of Allergy and Infectious Diseases (NIAID)
National Institutes of Health (NIH)
Department of Health and Human Services (DHHS)
Bethesda, Maryland, USA

STUDY PRODUCTS PROVIDED BY

Vaccine Research Center (VRC)
NIAID, NIH, DHHS
Bethesda, Maryland, USA

September 21, 2023

Final
HVTN 303
Version 2.0

HVTN 303 enrolled (vaccinated) its first participant on August 15, 2022, with the goal to enroll 60 participants in the study. As of Dec 20, 2022, 44 participants were enrolled (no enrollments occurred after this date). Part A (Groups 1, 2, 3, 4, and 5) completed enrollment of 15 participants from August 15 to October 14, 2022.

Part B enrolled 29 participants from November 3 to December 20, 2022: Group 6 enrolled 10 ppts, all of whom received 1 vaccination; Group 7 enrolled 10 participants, 5 of whom received 2 vaccinations; Group 8 enrolled 9 participants, 6 of whom received 2 vaccinations. No participants received a 3rd vaccination.

Over time, the PSRT observed trends in local and systemic reactogenicity (grade 3 fever, grade 3 injection site erythema, and/or induration/swelling), unsolicited adverse events (urticaria, rash, and serum sickness), and temporary increases in absolute eosinophil counts (AECs) post-vaccination. Certain of these events resulted in pauses in all vaccinations, and the PSRT requested the HVTN Safety Monitoring Board (SMB) perform an ad hoc review of all safety data. Following this review on January 11, 2023, the SMB recommended that all vaccinations in the study be permanently discontinued, and that participants be continued in safety follow-up, and these recommendations were implemented.

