2.6 Assessment of Immunogenicity

Vaccinations were stopped on January 13, 2023, resulting in most (33) participants receiving only 1 vaccination and eleven participants in Groups 7 and 8 receiving 2 vaccinations. Specimens to evaluate immunogenicity were collected at baseline and at the specified timepoints after the administration of product until March 13, 2023, when the FDA informed DAIDS that the IND has been placed on Clinical Hold and confirmed that all protocol-related activities must cease except for any participant safety follow-up assessments. The primary immunogenicity time point, after the changes to the vaccination and collection schedule, remains 2 weeks after the last vaccination, however participants only received 1 or 2 vaccinations. Antibody titers will be measured by Electrochemiluminescence (ELICA) using a Meso Scale Discovery (MSD) platform for all participants with one or two vaccinations in Groups 5, 6, 7 and 8.

Additional exploratory assays to assess humoral and cellular immune responses may be performed, including B cell response and neutralization antibody assays.

A specimen collection has been added at approximately 10 months post the

Specimens to evaluate immunogenicity will be collected at baseline and at specified time points throughout the study after the administration of product. HIV-specific humoral immune responses will be assessed by neutralization antibody assays. The primary immunogenicity time point is 2 weeks after the last vaccination.

Trimer 4571- and Trimer 6931-specific antibody titers will be measured by Electrochemiluminescence (ELICA) using a Meso Scale Discovery (MSD) platform. Other exploratory assays to assess humoral and cellular immune responses may be performed with stored samples.

Measurements of antibody, B-cell and T-cell responses may be assessed from stored samples for timepoints throughout the study as exploratory evaluations. This includes a number of high-throughput functional assays and high-throughput biophysical profiling tools to comprehensively characterize the humoral immune response elicited by vaccination regimens.

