7.1 Vaccine Regimen

The schedule of study product administration is shown in [Section 1.5](#) and additional information is given below.

Part A

Group 1

Treatment 1 (T1):

25 mcg FP Conjugate Vaccine (FP8v1-rTTHC; VRC-HIVVCP0108-00-VP) + 20% dose/volume (d/v) Adjuplex, to be administered as 0.8 mL, divided into 2 syringes (0.4 mL each), intramuscularly at Week 0.

Group 2

Treatment 2 (T2):

200 mcg FP conjugate vaccine (FP8v1-rTTHC; VRC-HIVVCP0108-00-VP) + 20% dose/volume (d/v) Adjuplex, to be administered as 0.8 mL, divided into 2 syringes (0.4 mL each), intramuscularly at Week 0.

Group 3

Treatment 3 (T3):

100 mcg Trimer 6931 (HIV-1 Trimer 6931 Vaccine; VRC-HIVRGP0106-00-VP) + 20% dose/volume (d/v) Adjuplex, to be administered as 0.8 mL, divided into 2 syringes (0.4 mL each), intramuscularly at Week 0.

Group 4

Treatment 4 (T4):

200 mcg Trimer 6931 (HIV-1 Trimer 6931 Vaccine; VRC-HIVRGP0106-00-VP) + 20% dose/volume (d/v) Adjuplex, to be administered as 0.8 mL, divided into 2 syringes (0.4 mL), intramuscularly at Week 0.

Group 5

Treatment 5 (T5):

200 mcg Trimer 4571 (HIV-1 Trimer 4571 Vaccine; VRC-HIVRGP096-00-VP) + 20% dose/volume (d/v) Adjuplex, to be administered as 0.8 mL, divided into 2 syringes (0.4 mL each), intramuscularly at Week 0.

Part B

Group 6

Treatment 6 (T6):

200 mcg Trimer 4571 + 20% dose/volume (d/v) Adjuplex, to be administered as 0.8 mL, divided into 2 syringes (0.4 mL each), intramuscularly at Weeks 0 and 12.

~~200 meg Trimer 6931 + 20% dose/volume (d/v) Adjuplex, to be administered as 0.8 mL, divided into 2 syringes (0.4 mL each), intramuscularly at Week 24.~~

~~100 meg Trimer 4571 + 100 meg Trimer 6931 + 20% dose/volume (d/v) Adjuplex, to be administered as 0.8 mL, divided into 2 syringes (0.4 mL each), at Weeks 36 and 48.~~

Group 7

Treatment 7 (T7):

200 mcg FP conjugate vaccine + 20% dose/volume (d/v) Adjuplex, to be administered as 0.8 mL, divided into 2 syringes (0.4 mL each), at Weeks 0 and 4 and 8.

~~200 meg Trimer 4571 + 20% dose/volume (d/v) Adjuplex, to be administered as 0.8 mL, divided into 2 syringes (0.4 mL each), intramuscularly at Weeks 12 and 24.~~

~~200 meg Trimer 6931 + 20% dose/volume (d/v) Adjuplex, to be administered as 0.8 mL, divided into 2 syringes (0.4 mL each), intramuscularly at Week 36.~~

~~100 mcg Trimer 4571 + 100 mcg Trimer 6931 + 20% dose/volume (d/v)
Adjuplex, to be administered as 0.8 mL, divided into 2 syringes (0.4 mL each), at
Week 48.~~

Group 8

Treatment 8 (T8):

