8.3 Reactogenicity Assessments

Pre-Vaccine Administration: Medical history and evaluations including vital signs and planned injection site evaluation are performed prior to each vaccine administration.

Post-Vaccine Administration Follow-Up in Clinic: Following each vaccine administration, participants will be observed for a minimum of 30 minutes post injection, vital signs will be recorded, the injection site will be inspected for

evidence of local reaction, and any evidence of systemic symptoms will be assessed. Participants will be contacted on the day after each study injection as indicated on the Schedule of Procedures ([Appendix A](#), [Appendix B](#), [Appendix C](#) and [Appendix D](#)).

Post-Clinic Follow-Up: Participants are asked to record symptoms on a daily basis using an electronic participant diary. Signs and symptoms considered to represent reactogenicity from the vaccine include systemic events of increased body temperature, fatigue, generalized myalgia, generalized arthralgia, headache, chills, nausea, and local events at the injection site, including pain/tenderness, induration, erythema, and bruising. Participant diaries will be reviewed by a clinician and reconciled for accuracy and completeness.

Participants will be given a thermometer for oral temperature measurement, a ruler, and provided access to the electronic diary. Participants will be encouraged to use the preferred electronic diary but will have the option to use a paper diary. The paper diary, if used, will be transcribed into the study database and stored in the participant file for monitoring purposes. The participant will use the diary to record daily their highest temperature as well as local and systemic signs and symptoms for 10 full days following each study vaccination. Participants will be provided training on diary completion, proper thermometer usage, and the use of the measuring device to measure any injection site induration and/or erythema.

In LOA #3 for protocol version 1.0 (distributed to the sites on Dec 14, 2022) the reactogenicity assessment period was increased from 7 days to 10 days. However, as vaccinations were permanently discontinued on January 13, 2023, the change in post-vaccine reactogenicity assessment period was no longer applicable and was not implemented. The reactogenicity assessment period of the previously vaccinated participants remained 7 days following vaccine administration.

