#### **10.4.1 Reactogenicity**

The number and percentage of participants experiencing each type of reactogenicity sign or symptom will be tabulated by severity and treatment arm in Part A and Part B and the percentages displayed graphically by arm. For a given sign or symptom, each participant's reactogenicity will be counted once under the maximum severity for all injection visits. In addition, to the individual types of events, the maximum severity of local pain or tenderness, induration or erythema, and of systemic symptoms will be calculated. Kruskal-Wallis tests will be used to test for differences in severity across arms and Wilcoxon rank sum test will be used to test for difference in severity between 2 arms in Part B.

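### Part B reactogenicity tests use the maximum over all injections, but 0/10, 5/10 and 6/9 participants had a second one, so contrasts with Group 6 mix product with number of injections

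*Protocol*

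**What the plan says.** For each sign or symptom, Protocol 6.5.3.1 states that a participant's "reactogenicity will be counted once under the maximum severity for all injection visits". SAP 10.4.1 repeats this and adds the tests: "Kruskal-Wallis tests will be used to test for differences in severity across arms", with Wilcoxon rank sum tests between two arms in Part B. Protocol 6.5 and SAP 10.1 analyse everyone as randomized, whatever number of vaccinations was received. Protocol 3.1 frames the safety objective in terms of regimens.

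The Version 2.0 summary at the front of the protocol gives the exposure in the first two Part B arms: "Group 6 enrolled 10 ppts, all of whom received 1 vaccination; Group 7 enrolled 10 participants, 5 of whom received 2 vaccinations". In the third arm, Group 8, it reports two injections for 6 of the 9 people enrolled. Nobody had a third. On the solicited period, Protocol 8.3 says: "The reactogenicity assessment period of the previously vaccinated participants remained 7 days following vaccine administration".

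SAP 11.2 lists maximum reactogenicity summaries and a table of product administration frequencies. SAP 11.3 lists severe reactions, and moderate or worse erythema and induration, for the SMB reports. No listed title refers to injection number.

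**The concern.** Group 6 participants had one chance to react; about half of Group 7 and two thirds of Group 8 had two. The summary measure can only rise with a second injection. A Group 7 or 8 excess over Group 6 may therefore come from the product, from the extra injection, or from both, and the planned output cannot tell these apart. The Kruskal-Wallis test has the same problem; Group 7 v Group 8 is little affected.

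These are the only formal between-arm tests planned on the primary safety endpoint, since Protocol 6.5.3.2 rules out formal testing of AEs. Protocol 2.5 treats Group 6 as the control arm for Groups 7 and 8, so these are the contrasts a reader will look for. No decision rule depends on them; what is at stake is how the final safety report is read.

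**Working it through.** **Counts.** Two injections: 0 + 5 + 6 = 11. One injection: 44 − 11 = 33. Both match Protocol 2.6, which reports 33 participants with one and "eleven participants in Groups 7 and 8 receiving 2 vaccinations".

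**Exposure.** Injections given in Groups 6, 7 and 8: 10, 10 + 5 = 15, and 9 + 6 = 15. At 7 solicited days each, that is 70, 105 and 105 days, or 7.0, 10.5 and 11.7 per participant. Exposure was equal at the first injection: all 29 received one Week 0 dose of 0.8 mL in two syringes with 20% Adjuplex (Protocol 7.1), differing only in antigen.

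**Why Group 6 has none.** Its second dose was due at Week 12, against Week 4 in Groups 7 and 8. The first Part B enrollment, November 3, 2022, plus 84 days is January 26, 2023, after the January 13 stop. The zero reflects schedule and stop date, not tolerance.

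**Shift in percentages.** Take the same independent per-injection risk p in every arm and let f be the share with a second injection. The share with at least one event is p + f·p(1 − p). At p = 20%:

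- Group 6: 20%
- Group 7: 20 + 0.5 × 16 = 28%
- Group 8: 20 + (6/9) × 16 = 30.7%

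For a grade 3 risk of 5–20% per injection, the expected Group 8 minus Group 6 gap is 3.2–10.7 points at within-person correlation 0, 2.5–7.5 at 0.5 and 1.7–4.7 at 0.8.

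**Test behaviour with identical products.** The documents give no per-injection rates or within-person correlation for these products, so both are assumed:

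- 40,000 simulated trials per scenario; n = 10, 10 and 9; second injections to 0, 5 and 6 at random.
- Grade shares (none/1/2/3) of 50/30/15/5, 30/35/25/10 or 20/30/30/20%, equal in all arms and at both injections.
- The two injections linked by a latent normal.
- Tie-corrected Wilcoxon (normal approximation with continuity correction) and Kruskal-Wallis over the three Part B arms.
- Two-sided 0.05, taken from Protocol 6.5.4.1, since no level is given for reactogenicity.

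| Rejection rate | Corr. 0 | Corr. 0.5 | Corr. 0.8 |
|---|---|---|---|
| 6 v 8 | 10.0–10.3% | 6.9–7.1% | 5.3–5.6% |
| 6 v 7 | 7.6–7.8% | 5.8–6.0% | 5.0–5.1% |
| Kruskal-Wallis | 8.4–8.9% | 6.1–6.5% | 5.2–5.4% |
| Share of 6 v 8 rejections with Group 8 worse | 98% | 92–93% | 82–84% |

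Group 7 v 8 stays at 3.9–4.4%. First-injection data give 4.2–4.7%, with Group 8 worse in 50–52% of the 6 v 8 rejections.

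**If second injections are worse in every arm.** A second simulation used first-injection shares of 40/35/20/5 or 20/30/30/20% and no continuity correction. With equal injections, 6 v 8 rejects in 5.9–11.2%. With second injections worse by 0.5 latent SD it rejects in 10.7–18.9%, and by 1 SD in 21–32%. The first-injection test for 6 v 8 stays at 4.5–5.1%.

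**Guide to the correlation.** The therapeutic Trimer 4571 trial with alum in Protocol 2.10.1.2 reports 15 participant-symptoms over 7 systemic symptoms in 16 people, 3 of them after both the first and second dose. The per-dose rate is 18/224 = 8.0%. Both doses occur in 3/112 = 2.7%, against 0.65% if independent. The tetrachoric correlation is about 0.56. Correlation 0 is thus an outer bound.

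**The case against.** The strongest reply is that the plan contains no error. The objective concerns regimens, and analysis is as randomized regardless of doses received. The groups were always to have 5, 7 and 6 injections, so the maximum was a whole-regimen summary from the start. That stands, and is why the planned test should stay. It does not explain 0/10 against 5/10 and 6/9, which the stop date produced.

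The size may also be small. At correlation 0.8 with equal injections the rejection rates barely exceed 5%. A false finding of Group 8 as worse then occurs in about 4.3–4.7% of trials (82–84% of 5.3–5.6%), against about 2.1–2.4% on first-injection data (50–52% of 4.2–4.7%). This stands too. The correlation guide is crude: people with HIV, alum, active and control recipients mixed, some with a third dose, and only three repeat reports.

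Existing outputs help in part. The administration-frequency table should reveal the imbalance, and the SMB listings show the worst reactions. Section 11 of the SAP gives titles only, so some content has to be inferred. But no title promises severity by injection number and arm.

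Extra unadjusted tests have a price. The chance of at least one false 6 v 8 result rises from about 5.4% to 6.6% (correlation 0.8), 7.0% to 8.6% (0.5) or 10% to 12% (0). This cost is real but small, in a plan that makes no multiplicity adjustment for safety endpoints.

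Second doses might have gone mainly to people who tolerated the first. When grade 3 first-dose reactors were simulated as last in line for dose 2, rejection did not fall (5.6–16.2%).

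**Conclusion.** The concern holds. The direction follows from the definition of a maximum and needs no assumption: contrasts with Group 6 and the three-arm test lean towards showing Groups 7 and 8 as more reactogenic. The size rests on the assumed severity shares, the within-person correlation and second injections resembling first ones. Under those assumptions it runs from negligible inflation at correlation 0.8 to a doubling of the nominal 5% for 6 v 8 at correlation 0. It is larger if second injections are worse.

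The plan already separates responses after the first and second vaccination for immunogenicity (Protocol 6.2.1) but not for reactogenicity. This should be fixed, as a matter of interpretation; the planned test is not invalid.

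**What to change.** In Protocol 6.5.3.1 and SAP 10.4.1:

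1. Keep the all-injections maximum and its tests, labelled 'regimen as delivered, unequal number of injections'.
2. Add the same Kruskal-Wallis and Wilcoxon tests on maximum severity after vaccination 1 (10, 10 and 9 participants) as the analysis for comparing products.
3. Tabulate severity after vaccination 2 descriptively, with denominators 5 (Group 7) and 6 (Group 8).

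The first-injection test should not replace the planned one. If only second injections were worse in Group 8, by 1–1.5 latent SD at correlation 0.5–0.8, the planned test rejects in 20–40% of trials and a first-injection test in 4–5%. For the same reason, and given 9–10 per arm, a null first-injection result should not be read as showing no product difference.

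The cost is SAP wording, one label and one stratifying variable in existing tables, with no new data. The downside is a few more tables and one more set of unadjusted tests, added after vaccination ended in an open-label trial; the report should say so.

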6.5.3.2 AEs and SAEs

AEs will be summarized using Medical Dictionary for Regulatory Activities (MedDRA) System Organ Class and preferred terms. Tables will show by treatment arm (in Part A and Part B) the number and percentage of participants

experiencing an AE within a System Organ Class or within preferred term category by severity or by relationship to study product. For the calculations in these tables, a participant with multiple AEs within a category will be counted once under the maximum severity or the strongest recorded causal relationship to study product. Formal statistical testing comparing arms is not planned since interpretation of differences must rely heavily upon clinical judgment.

A listing of SAEs reported to the Division of AIDS (DAIDS) Regulatory Support Center (RSC) Safety Office will provide details of the events including severity, relationship to study product, time between onset and last vaccination, and number of vaccinations received.

6.5.3.3 Local laboratory values

Box plots of local laboratory values will be generated for baseline values and for values measured during the course of the study by treatment arm (Part A and Part B) and visit. Each box plot will show the first quartile, the median, and the third quartile. Outliers (values outside the box plot) will also be plotted. If appropriate, horizontal lines representing boundaries for abnormal values will be plotted.

For each local laboratory measure, summary statistics will be presented by treatment arm and time point, as well as changes from baseline for post enrollment values. In addition, the number (percentage) of participants with local laboratory values recorded as meeting Grade 1 AE criteria or above as specified in the Division of AIDS Table for Grading the Severity of Adult and Pediatric Adverse Events (Section 9.1) will be tabulated by treatment arm for each post vaccination time point. Reportable clinical laboratory abnormalities without an associated clinical diagnosis will also be included in the tabulation of AEs described above.

